infection rapidly spread throughout the northern region. A decade later, this severe *S. mansoni* epidemic was followed by a shift towards *S. haematobium* infection, which also reached record prevalences. Today, schistosomiasis is still highly endemic in Senegal, despite national control efforts. Both *S. mansoni* and *S. haematobium* are wide-spread, resulting in a large number of people with mixed infections in the communities ⁷.

Since the 1970s, treatment schistosomiasis has relied almost exclusively on praziquantel (PZQ). PZQ has demonstrated good efficacy ¹ in a meta-analysis of 55 comparative and non-comparative trials involving > 19,000 participants, of whom 68% were school-age children ⁸; results can be summarized as follows:

- For *Sh* infection, the WHO-recommended 40 mg/kg single dose of PZQ achieved a cure rate (CR) of 77.1% (95% confidence interval [CI] 68.4-85.1%; 2,645 participants/20 studies) and a mean egg reduction rate (ERR) of 94.1% (1,957 participants/19 studies).
- For *Sm* infection, the WHO-recommended 40 mg/kg single dose of PZQ achieved a CR of 76.7% (95% CI 71.9-81.2%; 6,377 participants/45 studies) and a mean ERR of 86.3% (5,546 participants/39 studies).
- For mixed Sh/Sm infection, CR was 63.5% (95% CI 48.2-77.0%; 379 participants/6 studies).

Another meta-analysis comparing school-age and preschool-age children in 47 comparative/noncomparative studies showed similar efficacy results in both age groups ⁹. The WHO has set a tentative ERR threshold of 90% as an indicator of optimal efficacy ¹⁰. In a systematic review of 10 studies, CR and ERR of *Sm* infection increased with repeated PZQ administrations, but such an effect was not observed for *Sh* ¹¹.

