2.2. Secondary objectives

1. To evaluate the safety and cumulative efficacy of two additional courses of AM (at 6-week intervals each) for the treatment of schistosomiasis, compared to a single course of AM, and compared to the standard PZQ regimen (control arm).

Endpoint measures:

- Efficacy: CR, as assessed by microscopy, after the second and after the third AM administration (at week 10 and 16, 24 and 48 see study flowchart),
- Safety: Frequency and pattern of AEs and SAEs up to 4 weeks after the second and third AM administration.
- 2. To determine the egg reduction rate (ERR) obtained after single and repeated courses of AM compared to the standard PZQ regimen.
 - Endpoint measure: ERR after administration of PZQ and after each AM course (at week 4, 10, 16, 24 and 48 see study flowchart).
- 3. To determine the parasitological efficacy of single and repeated courses of AM by *Schistosoma* species and by infection intensity.

Endpoint measures: CR and ERR by initial *Schistosoma* infection intensity after PZQ administration and single and repeated courses of AM. (measured at week 4, 10 and 16 after first AM administration)

- 4. To assess the impact of repeated AM courses on schistosomiasis-related morbidity. Endpoint measures: Prevalence and severity of general and organ-specific schistosomiasis morbidity (as assessed by clinical evaluation, ultrasound, point-of-care morbidity markers and hemoglobin level) at week 24 and week 48 compared to baseline and compared to the control arm.
- To determine the diagnostic performance of novel schistosomiasis antigen- and DNA-based diagnostic assays to monitor antischistosomal treatment response.
 Endpoint measures: Sensitivity and specificity of the different conventional and novel diagnostic tests at baseline and at defined time points after treatment compared to conventional microscopy, and to composite reference standards.

6. To determine the effect of repeated AM courses on prevalence of *P. falciparum* infection as well as on incidence and morbidity of clinical malaria in school-age children with schistosomiasis.

Endpoint measures:

- Prevalence of malaria infection, as assessed by molecular testing of dried blood spots at baseline and week 24 and 48.
- Incidence of clinical malaria, as assessed by the number of incident malaria cases diagnosed through passive case detection during the study period (by standard malaria rapid tests and molecular diagnostics on dried blood spots).

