5.4. Laboratory procedures

5.4.1. Field tests

Microscopy

Parasitological examination of urine and stool by microscopy will be applied for the detection of *Sh* and *Sm* eggs to assess the primary endpoint (treatment efficacy), since it remains the WHO-established standard for diagnosis of schistosomiasis and assessment of treatment response. For each participant, two urine and two stool samples will be collected at two different days. Per feces sample, two Kato-Katz slides of 25 mg fecal material will be prepared and microscopically examined for *S. mansoni* eggs; each urine sample will be analyzed by the standard filtration technique for the detection of *S. haematobium* eggs. *Sm* and *Sh* infection intensity (average number of eggs per 25 mg gram of stool and per 10 ml of urine respectively) will be determined to determine the intensity of the infection according to WHO criteria ⁷⁴. Microscopy will be performed in the laboratory of the Public Health

facility in Richard Toll by experienced lab technicians, after specific training from an ITM expert. Other intestinal parasites detected by the two methods will also be recorded. For quality control, a random representative number of the slides read per day will be re-read by a second microscopist and the results will be compared for quality control. In case of discordant results, a third observation will be required to validate the result.

POC-CCA

A lateral flow immunochromatographic point-of-care assay (POC-CCA) will be used for the detection of *Schistosoma* circulating cathodic antigens in urine. The commercially available rapid immunochromatographic dipstick will be used (Rapid Medical Diagnostics, Pretoria, South Africa) and tests will be performed according to the manufacturer instructions. Briefly, 2 drops of urine will be transferred into the cassette and the results will be read after 20 minutes. The results will be categorized as negative or positive (trace CCA results will be considered positive) and for the positive, based on the intensity of the band, a concentration of the sample will be estimated in ng/ml (data unpublished), as a semi-quantitative measure of intensity of infection.

Urine reagent strip test

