8.2. Variables of interest

Primary

The primary variables to evaluate are:

- The parasitological cure rates (proportion of subjects negative for both *Schistosoma* species assessed by microscopy over total number in each arm) for AM and PZQ at week 4 after inclusion.
- The patient counts with drug-related adverse events and serious adverse events up to 4 weeks after AM and PZQ administration.

Secondary:

The secondary variables to evaluate are:

- The proportion of cured subjects (CR) of the two different arms at week 10, 16, 24 and 48 (see flowchart).
- The count of patients reporting any form of adverse event up to 4 weeks after each study drug administration.
- The egg reduction rate (ERR) at weeks 4, 10, 16, 24 and 48 (see flowchart). The ERR will be expressed as the percentage of eggs present in each subject at each time point over the number of eggs at baseline.
- The cure rate and egg reduction rate at weeks 4, 10 and 16 after first treatment administration by *Schistosoma* species and by intensity of infection.
- The result of the classic and novel diagnostic tests at baseline and at different time points, as well as a-composite reference standards.
- Clinical and laboratory characteristics related to schistosomiasis-related morbidity at baseline and at weeks 4, 10, 16, 24 and 48
- Prevalence of malaria infection at baseline and at weeks 24 and 48
- The incidence of clinical malaria during the study until week 48
- Counts of cases of anemia both pooled and by severity levels at baseline, week 24 and week
 48
- Binary variables indicating the existence of any or specific types of resistance in the sample size and among the incident malaria cases

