8.3.4. Secondary and tertiary analysis

Secondary analyses

The efficacy of the two treatments over time will be assessed both by calculating the two-sided 95% CI for the difference in proportions of cured subjects at different time points as well as using a mixed effects logistic regression model. Schistosomiasis infection at specific time points will be used as the outcome and treatment and visit as independent variables with a random intercept. Subsequent analyses of the cure rate per *Schistosoma* species and by *Schistosoma* infection intensity will be analyzed in a similar way including those characteristics as covariates in the model. The analyses for

ERR will be done using a linear mixed effects model with a random intercept and a logit link function separately for each *Schistosoma species*. All comparison of proportions will be done using the Chi-square or Fisher's exact test and comparison of continuous characteristics will be done using the Wilcoxon rank sum test. The sensitivity of a specific diagnostic test will be calculated as the proportion of children with schistosomiasis (based on the reference standard used) who have a positive result. The specificity of a diagnostic test will be calculated as the proportion of children without schistosomiasis who have a negative result. The positive predictive value of a diagnostic test will be calculated as the proportion of children with schistosomiasis with a positive result. The negative predictive value of a diagnostic test will be calculated as the proportion of people with a negative result who do not have schistosomiasis. These different values of both novel and classic diagnostic tests will be calculated together with 95% confidence intervals. Composite reference standards will be created by the investigators of the study and will be used as a comparison. An alternative reference standard will be calculated using latent class analysis methodology. The prevalence and patterns of resistant mutations between the two treatment groups will be compared using Chi-square or Fisher's exact test.

Safety analyses

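### Cure by species is modelled with an any-species infection outcome, so the cure part of secondary objective 3 is misstated or only partly answered

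*Protocol*

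**What the plan says.** Secondary objective 3 (Protocol, 2.2) is "To determine the parasitological efficacy of single and repeated courses of AM by" Schistosoma species and by infection intensity. Section 8.2 lists the matching variable as "The cure rate and egg reduction rate at weeks 4, 10 and 16 after first treatment administration by" species and intensity.

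The only definition of cure that 8.2 gives for the trial's own variables is attached to the primary week 4 endpoint: "proportion of subjects negative for both" species by microscopy.

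Section 8.3.4 then sets up the longitudinal cure model: "Schistosomiasis infection at specific time points will be used as the outcome and treatment and visit as independent variables with a random intercept". Cure per species and by intensity "will be analyzed in a similar way including those characteristics as covariates in the model". The sentence that follows treats ERR differently, with a mixed model "and a logit link function separately for each" species.

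The raw data are specific to species. Under 5.4.1, S. mansoni eggs are sought on Kato-Katz slides of stool, and "each urine sample will be analyzed by the standard filtration technique for the detection of" S. haematobium eggs.

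**The concern.** A question about efficacy against one species needs an outcome for that species. The text keeps a single outcome, infection with either species, and moves species to the right-hand side of the model as a description of the child. The model then estimates how often children of a given baseline type become free of both species. It does not estimate how often a given species is cleared.

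The difference matters only if mixed infections or newly detected second infections are common, and the protocol expects both to be possible. Sections 1.1.1 and 4.1 describe mixed infections as frequent in the area, and inclusion requires eggs in urine, stool or both (4.2). Section 1.1.1 gives about 5 to 7 weeks for larvae to mature and describes PZQ as very weak against immature stages. Section 1.1.2 notes that microscopy misses light infections, and follow-up runs through the rainy season (section 3). Only the artesunate-mefloquine (AM) arm is dosed again, at weeks 6 and 12, so new detections of the other species could also differ between arms.

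What is at stake is the cure half of one secondary objective.

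**Working it through.** **Step 1. What each outcome does with the same child**

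| Baseline | Follow-up microscopy | Any-species outcome | S. haematobium cure | S. mansoni cure |
|---|---|---|---|---|
| Mixed | urine negative, stool positive | failure | yes | no |
| Mixed | urine positive, stool negative | failure | no | yes |
| S. haematobium only | urine negative, stool newly positive | failure | yes | not applicable |
| S. mansoni only | stool negative, urine newly positive | failure | not applicable | yes |

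The protocol does not say how the species covariate is coded.

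- *Two indicators (each species yes/no):* the mixed child in rows 1 and 2 counts against both species.
- *Three levels (S. haematobium only, S. mansoni only, mixed):* the child counts as a failure in the mixed level, and clearance of a single species within mixed infection is not estimated.
- *Either coding:* rows 3 and 4 are failures. With species as a main effect only, there is one common treatment effect and none by species.

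**Step 2. Inputs for an illustration**

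The protocol states no figure for this analysis, so there is none to reproduce. From 1.1.1, PZQ cure is 77.1% for S. haematobium and 76.7% for S. mansoni. For mixed infection the text reads "infection, CR was 63.5% (95% CI 48.2-77.0%; 379 participants/6 studies").

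Assumptions:
- The 63.5% means both species cleared; the protocol does not say how cure was defined there.
- The two single-species rates also hold within mixed infection.
- The share m of species-positive children who are mixed is 10% to 70%; the protocol gives no figure.

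**Step 3. Mixed children who clear exactly one species**

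- With 63.5% clearing both: 0.771 + 0.767 − 2 × 0.635 = 0.268, about 27%.
- If clearance were independent: both = 0.771 × 0.767 = 0.591, and exactly one = 1.538 − 2 × 0.5914 = 0.355, about 36%.

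**Step 4. Cure among species-positive children under the any-species outcome (mixed children pooled in)**

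Cure = (1 − m) × single-species rate + m × 0.635.

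| m | S. haematobium (own outcome 77.1%) | S. mansoni (own outcome 76.7%) |
|---|---|---|
| 10% | 75.7% | 75.4% |
| 30% | 73.0% | 72.7% |
| 50% | 70.3% | 70.1% |
| 70% | 67.6% | 67.5% |

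The shortfall for S. haematobium is m × 0.136, that is 1.4 points at m = 10% and 9.5 at m = 70%. For S. mansoni it is m × 0.132, that is 1.3 and 9.2 points. Under independence it reaches 12.6 and 12.3 points at m = 70%.

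**Step 5. How firm this is**

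With the two marginal rates fixed, the share clearing both can only lie between 0.771 + 0.767 − 1 = 0.538 and 0.767. The interval of 48.2% to 77.0% covers that whole range. The share clearing exactly one species could therefore be anywhere from 1.538 − 2 × 0.767 = 0.4% to 1.538 − 2 × 0.538 = 46.2%. Step 4 shows the mechanism and a central size, not a precise bias.

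**Step 6. The contrast between arms**

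Assume that AM equals PZQ on S. haematobium (77.1%), clears S. mansoni in only 55% (an assumed value), and that clearance is independent. The true S. haematobium difference is 0. The any-species difference among S. haematobium-positive children is m × 0.771 × (0.55 − 0.767) = −0.167 × m. At m = 20%, 40% and 60% this is −3.3, −6.7 and −10.0 points.

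**The case against.** The strongest reply is that the wording is loose rather than wrong. The reference to a similar way may mean only the same methods, a confidence interval and a mixed logistic model, applied to a cure rate already understood per species. The requirement of being negative for both species is attached to the primary variable. The general definition of cure in the footnote to 1.1.1, egg-positive children who become egg-negative, could be applied to each species. A binding statistical analysis plan is announced in section 8 and may settle the point. Some ambiguity does remain. But the text names the outcome, says where species enters, and writes a species split for ERR only. Nothing in the protocol supplies an outcome for cure of a single species.

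The coding objection also stands in part. A three-level covariate matches the three groups reported in 1.1.1. With it, mixed children are not pooled into either species, and the shortfall in step 4 of the working does not arise. A treatment-by-group interaction would then give arm differences in single-species children and in mixed children, which is a recognisable part of the answer. It would still not recover clearance of one species within mixed infection, and new eggs of the other species would still turn a single-species cure into a failure.

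A reader might infer that the trial could not tell which species AM treats. The documents do not support that: ERR is modelled by species, eggs are counted by species, randomization is stratified for species (4.4), and single-species children remain informative.

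**Conclusion.** The point holds as a defect in how cure is derived for secondary objective 3. As written, the plan does not yield cure by species. Clearance of one species in a mixed infection is never counted as a cure, newly detected eggs of the other species make a single-species child a failure, and a main-effect covariate gives no treatment effect by species. The cure part of the objective is therefore misstated (two indicators) or only partly answered (three levels).

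The size is illustrative. With the protocol's PZQ rates and the assumptions in the working, about 27% of mixed children clear exactly one species. Pooled species cure is about 1 to 10 points too low for a mixed share of 10% to 70%. The mixed share, the carrying over of single-species rates to mixed infection, and the meaning of the 63.5% are all assumed, and the effect of newly detected infections cannot be quantified from the protocol.

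A reader might go further and conclude that every partly cleared child is a failure for both species, or that AM's cure rate against S. haematobium will be understated by a large, known amount. The first needs a coding that the protocol never states. The second needs that pooling and also an AM cure rate for S. mansoni that the protocol does not give. The primary endpoint, its margin and its sample size are not affected.

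**What to change.** In 8.2 and 8.3.4, add two derived variables:

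- S. mansoni cure: stool egg-negative at the visit, among children with S. mansoni eggs at baseline.
- S. haematobium cure: urine egg-negative at the visit, among children with S. haematobium eggs at baseline.

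Mixed-infection children belong to both sets. Fit the cure model separately for each species, as already planned for ERR, with treatment and visit as now, and with that species' own baseline intensity and mixed-infection status as factors. Calculate the confidence intervals for differences in cure at each visit on the same sets. Keep negativity for both species as the primary endpoint.

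Settle this before the week 16 analysis of cure and ERR (8.3.6) is run and communicated.

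The cost is wording and slightly more analysis. Denominators per species are smaller than the full sample, so intervals will be wider. The two species results share the mixed children and are not independent. No new data are needed, since stool and urine are already read separately.

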4.3. Sample size

The sample size was calculated on the parasitological cure rate endpoint after the first course of AM, to test the hypothesis that AM is non-inferior to PZQ: at least a 65% cure rate with AM as compared to a 75% cure rate with PZQ according to the following rationale. We consider that a cure rate (CR) of 65% is clinically acceptable as threshold for non-inferiority for the AM combination, for the following reasons: a cure rate above 65% would be very satisfactory compared to all alternative drugs evaluated so far against schistosomiasis, and an efficacy slightly lower than that of PZQ would be largely compensated by the positive clinical effect due to concomitant malaria suppression. Note that this is likely to be marginal in North Senegal where malaria transmission is low, but this "dual" effect could be a major added-value in many other co-endemic regions with higher malaria transmission

Sample size was calculated by simulation to obtain 80% power. The required sample size is 300 schoolchildren per arm. To account for a 20% loss to follow up, the total number of children to be recruited will be 726 (363 per arm). With the same sample size, superiority of repeated courses of AM to PZQ (cure rate of at least 85% after 3 courses) can also be demonstrated with a similar power (i.e. secondary endpoint).

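### Section 8.3.4 defines the positive predictive value with the formula for sensitivity; the error is confined to that measure and can run in either direction

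*Protocol*

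**What the plan says.** Section 8.3.4 of the protocol defines four accuracy measures in consecutive sentences.

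- Sensitivity is "the proportion of children with schistosomiasis (based on the reference standard used) who have a positive result".
- Specificity is "the proportion of children without schistosomiasis who have a negative result".
- For PPV: "The positive predictive value of a diagnostic test will be calculated as the proportion of children with schistosomiasis with a positive result".
- NPV is "the proportion of people with a negative result who do not have schistosomiasis".

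The section then commits to all of them: "These different values of both novel and classic diagnostic tests will be calculated together with 95% confidence intervals". No other part of the protocol defines PPV. Secondary objective 5 in section 2.2 names a narrower endpoint: "Sensitivity and specificity of the different conventional and novel diagnostic tests at baseline and at defined time points after treatment".

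**The concern.** The sensitivity and PPV sentences name the same denominator (infected children) and the same numerator (infected children who test positive). A predictive value should start from the test result, as the NPV sentence does, so the two predictive values rest on different bases.

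Diagnostic accuracy is one of the trial's stated hypotheses (sections 1.2 and 8.1). Section 5.4.2 asks for it for each test, in each arm and at each time point. After treatment, PPV tells a user how often a positive result reflects infection that the reference confirms. A quantity computed only among infected children cannot say that, because children who are uninfected but test positive never enter it.

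**Working it through.** The protocol gives no PPV figure to reproduce, so the check compares the definitions and then illustrates the size.

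**Step 1: the definitions as 2×2 formulas.** TP, FP, FN and TN are counted against whichever reference standard is in use.

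| Measure | As worded in 8.3.4 | Standard formula |
|---|---|---|
| Sensitivity | TP/(TP+FN) | TP/(TP+FN) |
| Specificity | TN/(TN+FP) | TN/(TN+FP) |
| PPV | TP/(TP+FN) | TP/(TP+FP) |
| NPV | TN/(TN+FN) | TN/(TN+FN) |

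Three of the four agree. The PPV row repeats the sensitivity row.

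**Step 2: direction of the error.** The worded and true PPV share the numerator TP and differ only in FN against FP in the denominator. The worded value is too high when FP exceeds FN, that is when (1 − prev)(1 − Sp) > prev(1 − Se). It is too low when the inequality is reversed.

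**Step 3: inputs.**
- Prevalence after treatment: section 4.3 plans on "at least a 65% cure rate with AM as compared to a 75% cure rate with PZQ", so 25% to 35% would still be egg-positive at week 4.
- Prevalence at baseline against microscopy: about 100%, because eggs in urine or stool are an inclusion criterion (section 4.2).
- Sensitivity (Se) 70% to 90% and specificity (Sp) 70% to 95%: assumptions, not taken from the protocol.

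**Step 4: results**, with true PPV = prev·Se / [prev·Se + (1 − prev)(1 − Sp)].

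| Prevalence | Se | Sp | TP | FP | True PPV | As worded |
|---|---|---|---|---|---|---|
| 25% | 90% | 80% | 0.225 | 0.150 | 60% | 90% |
| 25% | 90% | 70% | 0.225 | 0.225 | 50% | 90% |
| 25% | 90% | 95% | 0.225 | 0.0375 | 86% | 90% |
| 25% | 70% | 95% | 0.175 | 0.0375 | 82% | 70% |
| 35% | 70% | 95% | 0.245 | 0.0325 | 88% | 70% |
| 100% (baseline) | 70% or 90% | any | 0.70 or 0.90 | 0 | 100% | 70% or 90% |

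Over prevalence 25% to 35% with the assumed Se and Sp ranges, the true PPV runs from 0.175/(0.175 + 0.225) = 44% to 0.315/(0.315 + 0.0325) = 91%. The worded formula returns only the assumed sensitivity. In the rows shown, it is 40 points too high at one extreme and, among the post-treatment rows, 18 points too low at the other.

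**The case against.** The strongest reply is that this is a drafting slip with little consequence. The measure carries a standard name, the other three definitions are right, and with goodwill the sentence can be parsed as the share infected among children who test positive. Section 8 hands the analysis to a binding SAP, which was not available here and may word PPV properly. PPV is not a named endpoint, no data are lost, and PPV can be recovered from sensitivity, specificity and prevalence.

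Most of that stands, and it limits the weight of the point. It does not rescue the sentence: the sensitivity definition uses nearly the same phrase with infected children as the denominator, and the protocol fixes a formula here instead of leaving it to the SAP.

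A reader might infer three stronger things that the document does not support.

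- *That correction will lower the PPVs.* Steps 2 and 4 show that it can raise them. It does so at baseline against microscopy, and wherever specificity is close to 100%, as sections 1.1.2 and 5.4.2 describe for PCR.
- *That a poorly specific test would escape notice.* Specificity is correctly defined and is to be reported with a confidence interval for every test, so false positives would show there.
- *That the trial will certainly report sensitivity twice and no PPV.* That follows only if the sentence is applied literally, and the protocol alone cannot show that it will be.

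**Conclusion.** The PPV definition in section 8.3.4 is wrong as written. Applied literally, it makes PPV identical to sensitivity for every test, time point and reference standard. That conclusion needs no assumption beyond the natural reading of the sentence.

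The size and sign of the numerical error do rest on assumptions: the sensitivity and specificity values are illustrative, and the 25% to 35% prevalence comes from planning cure rates by microscopy. Under the composite or latent-class references that 8.3.4 also plans, prevalence could differ.

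The non-inferiority analysis, the sample size and the named diagnostic endpoint are unaffected. Severity is minor.

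**What to change.** Replace the PPV sentence in section 8.3.4 with one that conditions on the test result, for example: *PPV is the proportion of children with a positive test result who have schistosomiasis according to the reference standard used.* Check that the SAP uses the same definition.

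The cost is one sentence. No new data or further analyses are needed, and no other endpoint changes.
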